4. STUDY DESIGN

4.1 Study Design

This study is a prospective, single-arm, multicentre confirmatory study.

4.2 Number of Participants

A total of up to 75 participants presenting with urinary stones and meeting the inclusion/exclusion criteria will be recruited for this study. This will include male and female participants with urinary stone disease.

4.3 Eligibility Criteria

4.3.1 Inclusion Criteria

1. Participant is ≥ 18 years
2. Participants has voluntarily signed/dated the informed consent form.
3. Participant understands and accepts the study requirements.
4. Participant has one urinary stone eligible for treatment (minimum) that is:
 - a. apparent on a computed tomography (CT) scan within 14 days prior to study enrollment,
 - b. located within the renal pelvis or ureter, and,
 - c. is ≥ 3 mm in all dimensions
 - d. is ≤ 10 mm in maximum dimension and has area $<56 \text{ mm}^2$, as estimated by pre-procedure CT (area calculation: product of mathematical constant pi and the square of the radius for a stone appearing approximately circular on CT; product of long dimension and short dimension for a stone appearing oblong on CT)
5. Participants with additional stone(s) in one or both kidneys are admissible and must meet the following inclusion criteria:
 - a. Number of stones (≥ 3 mm) present on treated side is 2 or less
 - b. Untreated stones must not be anticipated to require treatment within 30 days of enrollment, as determined by the investigator

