4.4.4 Point of enrollment

Enrollment is defined as that time when the participant signs the informed consent form and is then eligible to begin screening assessments. Participants who fail to meet screening assessment requirements (see Section 6.1) will be counted as a screen failure and will not be treated with the ELS. Screen failures will be documented at the site on a screening log.

Each enrolled study participant will be assigned a unique participant identification number at the time of enrollment. This participant identification number will be retained throughout the study. Investigational site will keep a log that notes the participant's name and corresponding participant identification number. All electronic case report forms (eCRFs) will be tracked, evaluated, and stored using only the participant ID number. No personal identifying information will be included on the eCRFs.

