5. STUDY ENDPOINTS

5.1 Primary Endpoint

Treatment success: Proportion of study participants who are successfully treated following up to 2 ELS treatments [defined as absence of stones or with remaining fragments of less than 3 mm on the largest dimension by follow-up imaging through 30 day visit after last ELS procedure].

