5.2 Secondary Endpoints

- Proportion of participants with Serious Device and/or Serious Procedure-Related AEs from initial ELS Treatment through 30 days following last ELS treatment.
- Proportion of participants with Serious Device and/or Serious Procedure-Related AEs from initial ELS Treatment through 90 days following last ELS treatment.
- All AEs & SAEs from initial ELS Treatment through 30 days following last ELS treatment
- All AEs & SAEs from initial ELS Treatment through 90 days following last ELS treatment
- Participant satisfaction at 30 day follow-up following last ELS treatment

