6. STUDY VISIT SCHEDULE AND PROCEDURES

6.1 Screening

Screening for this study includes the following assessments. Refer to the Schedule of Assessments Table 2: Schedule of Events.

Confidential

Page 15 of 19

Study of an Enhanced Lithotripsy System in the Treatment Of Urinary Stone Disease (STONES)

Version 2.0, July 10, 2019

- Participants will undergo a CT scan within 14 days of the ELS procedure to estimate the approximate stone size (in mm), radiodensity and location (e.g. renal pelvis, distal ureter). Investigators should perform additional imaging prior to ELS treatment, particularly if symptoms have changed or if a participant is in the process of ureteral stone passage, because a change in stone position may influence treatment approach. This additional imaging can include KUB x-ray, renal/bladder US, or CT depending on investigator's discretion. If CT imaging is performed more than once, the CT imaging that occurs just prior to the first ELS procedure will be counted as baseline.
- The scout film acquired during the baseline CT is recommended to be used to document radiopacity for participants suspected with radiolucent stone(s). A KUB x-ray may be performed if the scout film is not available for this purpose.
- Participants will undergo a physical exam and medical history.
- For women of child-bearing age, participants will undergo a pregnancy test (if necessary).
- Participants will undergo a urinalysis and urine culture.
- Serum creatinine will be collected to review renal function.
- Prior to treatment, participant usage of pain medication (type, dose and frequency) will be documented, whether such pain medications were prescribed in connection with the scheduled study procedure or otherwise.
- Prior to treatment, participant usage of anticoagulants (type, dose and frequency) will be documented.
- Within 1 day of the ELS Treatment, study participants will also be asked to complete a pain questionnaire (pain score). The pain questionnaire may be completed on the same day as ELS Treatment before the treatment takes place.

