6.3.2 Scheduling

The additional ELS Treatment is recommended to be performed 30 days (\pm 14 days) from the index procedure (Day 0). When an additional ELS Treatment is performed, participants will repeat the Day 1, 2, 3, 7, 14 & 30 follow-up visits. The Day 90 Follow-up visit is expected to occur 90 +/- 21 days from the last ELS Treatment.

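### Criterion 5b looks ahead 30 days from consent, but the primary CT can fall 42 to 78 days after the first ELS, so a foreseeable procedure on another treated-side stone before that CT is not excluded

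*Combined protocol and SAP*

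**What the plan says.** Criterion 5 in Section 4.3.1 admits participants with additional kidney stones. Part (a) allows at most two stones of 3 mm or more on the treated side. Part (b) states: "Untreated stones must not be anticipated to require treatment within 30 days of enrollment, as determined by the investigator". The synopsis repeats part (b).

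The clock in part (b) starts at consent. Section 4.4.4 reads: "Enrollment is defined as that time when the participant signs the informed consent form and is then eligible to begin screening assessments".

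The primary outcome is tied to a different event, the last ELS procedure. Section 5.1 assesses success "by follow-up imaging through 30 day visit after last ELS procedure", and Section 6.2.6 sets that visit, with its CT, at 30 ± 4 days. Section 6.3.2 says "The additional ELS Treatment is recommended to be performed 30 days" (± 14 days) from the index procedure.

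Three other places bear on the point:

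- Section 6.3.1 requires participants to meet Section 4.3 again before a second ELS.
- Section 6.4 provides for recording non-ELS interventions, but only for stones selected for ELS treatment.
- Sections 11.1 and 11.3 define the analysis sets and the success rule. Neither mentions a procedure on a stone that was not treated with ELS.

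**The concern.** The entry rule and the endpoint run on different clocks. One is a fixed 30 days from consent; the other moves with the last ELS. If a ureteroscopy or shockwave treatment of a second stone on the same side is already foreseen, but for after the 30 days, the participant satisfies 5b and the procedure may still come before the primary CT.

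The CT would then no longer show the effect of ELS alone. The protocol itself supplies the mechanism: Section 1.1 describes the ureteral manipulation involved in ureteroscopy, and Section 7.1 notes that instruments can push a stone back into the kidney. Fragments of the ELS-treated stone could be cleared or displaced, so the misclassification could go either way.

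The trial has a single arm, so no control group would share the disturbance. The success threshold is also a count, so at the boundary one participant decides the result.

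**Working it through.** **The plan's own threshold (Section 11.6).** The plan needs 37 successes in 58 against a performance goal of 0.50. The exact two-sided 95% lower limit for 37/58 is 0.501. The plan prints 0.502, and both exceed 0.50. For 36/58 the lower limit is 0.484, which fails. One participant classified differently at the boundary therefore changes the conclusion.

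**Inputs for the windows**

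- 5b horizon: 30 days from consent (Sections 4.3.1 and 4.4.4).
- Second ELS: day 30 ± 14, that is day 16 to day 44 after the first ELS (Section 6.3.2; recommended, not mandatory).
- Primary CT: 30 ± 4 days, that is 26 to 34 days, after the last ELS (Section 6.2.6).
- Delay from consent to first ELS, L: not stated. Eligibility requires a stone "apparent on a computed tomography (CT) scan within 14 days prior to study enrollment", and Section 6.1 says "Participants will undergo a CT scan within 14 days of the ELS procedure". If one CT serves both rules, L can be 0 to 14 days. This range is an assumption: repeat CT is allowed, so no explicit cap exists.

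Counted from the first ELS, 5b reaches day 30 − L: day 30 if L = 0, day 16 if L = 14.

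**Primary CT, in days after the first ELS**

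| Course | Earliest | Latest |
|---|---|---|
| One ELS | 26 | 34 |
| Two ELS, recommended schedule | 16 + 26 = 42 | 44 + 34 = 78 |

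**Days by which the CT falls beyond 5b**

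| Course | L = 0 | L = 14 |
|---|---|---|
| One ELS, latest CT | 34 − 30 = 4 | 34 − 16 = 18 |
| Two ELS, earliest CT | 42 − 30 = 12 | 42 − 16 = 26 |
| Two ELS, latest CT | 78 − 30 = 48 | 78 − 16 = 62 |

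**Example.** Suppose a procedure on another treated-side stone is foreseen for day 35 after consent. It passes 5b. With one ELS on the day of consent, the CT is on days 26 to 34 and comes first, so there is no problem. With L = 7, the CT is on days 33 to 41 after consent and the procedure may precede it. With two ELS on the recommended schedule, the CT is on day 42 or later and the procedure always precedes it.

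**Does the re-check in Section 6.3.1 close the gap?** As worded, 5b still counts from enrollment. With L = 0 and the earliest second ELS on day 16, 30 − 16 = 14 days of the horizon remain, while the CT is 26 to 34 days away. From day 30 onward nothing remains.

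**The case against.** The strongest reply is that the exposed group is narrow. With one ELS on the day of consent the gap is at most 4 days. Criterion 5a leaves room for at most one untreated stone of 3 mm or more on the treated side, and a procedure on the other side would not alter the primary image. All of this stands, and it confines the point to treated-side stones and mainly to retreated participants.

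A second reply is that investigators would, in practice, look ahead afresh at the Section 6.3.1 re-check, and may judge a participant unsuitable for retreatment. That is plausible, but the text does not say it. Even a fresh 30 days from the second ELS would leave up to 34 − 30 = 4 days before the CT, and up to 44 − 30 = 14 days between the end of the first horizon and the second ELS (L = 0).

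A third is that an entry rule based on anticipation cannot prevent unplanned procedures. That is true. The rule can still remove the foreseeable ones.

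A reader might also infer three stronger points, which the documents do not support:

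- **That the safety endpoint runs to day 155.** Section 5.2 counts "Serious Device and/or Serious Procedure-Related AEs from initial ELS Treatment through 90 days following last ELS treatment". On the recommended schedule that is 44 + 90 = day 134. Day 155 (44 + 90 + 21) is the latest 90-day visit. AEs are collected to study exit, but that is not the endpoint window. Section 8.2 defines how related events are attributed, including a category for the effect of another device or drug, and the all-AE tables are descriptive.
- **That 5b was written to protect the endpoint and fails at it.** No rationale for 5b is given. It may serve only to keep out patients who need prompt care for another stone.
- **That 5b should therefore extend through the 90-day visit.** That is a debatable eligibility trade-off, which the safety endpoints as defined do not require.

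**Conclusion.** The concern holds for the primary endpoint and for untreated stones on the treated side. On the recommended retreatment schedule the primary CT falls 42 to 78 days after the first ELS, which is 12 to 48 days beyond the 5b horizon even with ELS on the day of consent. With one ELS the excess is at most 4 days plus the consent-to-ELS delay. Day 78 is not a hard maximum, because the timing of the second ELS is only recommended.

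No section excludes a foreseeable treated-side procedure in that interval or says how to analyse a participant who has one. The calculation shows that the opportunity exists, not how often it would arise. The documents give no frequency of untreated stones or of later procedures, so neither the size nor the direction of any bias can be stated. What makes the point worth acting on is a single-arm design with a one-participant margin at 37/58, set against a cheap remedy.

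**What to change.** In the synopsis and Section 4.3.1, split 5b by side. For untreated stones on the treated side, replace 30 days from enrollment with the primary endpoint window: no treatment anticipated before the 30-day CT after the last ELS procedure (about 80 days after the first ELS on the recommended schedule). Other untreated stones can keep the present wording. In Section 6.3.1, state that the re-check applies 5b forward from the second ELS to its 30-day CT.

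This governs enrollment and the eligibility re-check only. It does not bear on whether or when another stone is treated.

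Since an entry rule cannot cover unforeseen procedures or participants already enrolled, the separate SAP announced in Section 11.7 is the natural place for one sentence on how a participant with an intervening treated-side procedure is counted.

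The cost is amendment wording in three places. A few multi-stone candidates with a treated-side procedure already foreseen may not be enrolled; the documents do not allow their number to be estimated.

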4.3.2 Exclusion Criteria

1. Participant is less than 18 years of age or over 75 years of age

2. Participant is diagnosed with radiolucent stones
3. Participant has history of cystinuria
4. Participant has urine pH below 5.5
5. Participant has an untreated urinary tract infection
6. Participant is pregnant
7. Participant is a vulnerable individual (mentally disabled, physically disabled, prisoner, etc.)
8. Participant is enrolled in another research study or has previous participation within 30 days of enrollment.
9. Participant has planned general anesthesia during index procedure with American Society of Anesthesiologists (ASA) physical classification level of 3 or greater.
10. Participant has known sensitivity to possible medications used before, during, or after the ELS procedure, including but not limited to the following: sedative agents, general anaesthetics, topical anaesthetics, and opioid analgesics.
11. Participant has coagulation abnormality or taking prescription anticoagulants that cannot be stopped during treatment. Aspirin (ASA) usage will be discontinued at least 7 days prior to enrollment at the discretion of the attending physician.
12. Participant has mobility issues and is unable to comfortably lie still for up to 120 minutes or unable to roll from back to side.
13. Participant has known hypersensitivity to conductivity gel.
14. Participant has body mass index (BMI) ≥ 35 unless anticipated skin to stone distance (anticipated distance from site of ELS treatment head to stone per pre-operative CT) is < 135 mm.
15. Participant has an implanted spinal cord neurostimulator, intrathecal pump or any device that may interfere with energy transmission
16. Participant has open wounds, lesions, dermatitis, or ischemic tissues in the treatment area.
17. Participant has had a major surgery that removed tissue around the spinal cord (e.g. a laminectomy) within the treatment area.
18. Participant will undergo treatment of a stone located in the distal ureter and has previous hernia repair or surgical mesh implanted in the inguinal/hypogastric regions.

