	
9. Participant has planned general anesthesia during index procedure with American Society of Anesthesiologists (ASA) physical classification level of 3 or greater
 
10. Known sensitivity to possible medications used before, during, or after the ELS procedure, including but not limited to the following: sedative agents, general anaesthetics, topical anaesthetics, and opioid analgesics
 
11. Coagulation abnormality or taking prescription anticoagulants that cannot be stopped during treatment. Aspirin usage will be discontinued at least 7 days prior to enrollment at the discretion of the attending physician
 
12. Mobility issues - unable to comfortably lie still for up to 120 minutes or unable to roll from back to side
 
13. Known hypersensitivity to conductivity gel
 
14. Body mass index (BMI) ≥ 35 unless anticipated skin to stone distance (anticipated distance from site of ELS treatment head to stone per pre-operative CT) is < 135 mm
 
15. Implanted spinal cord neurostimulator intrathecal pump or any device that may interfere with energy transmission
 
16. Participant has open wounds, lesions, dermatitis, or ischemic tissues in the treatment area
 
17. Participant has had a major surgery that removed tissue around the spinal cord (e.g. a laminectomy) within the treatment area
 
18. Participant will undergo treatment of a stone located in the distal ureter and has previous hernia repair or surgical mesh implanted in the inguinal/hypogastric regions

Sample Size	Up to 75 participants will be enrolled to achieve approximately 58 participants that are evaluable for the primary endpoint
Enrollment period/Timeline	February 2019 through January 2020 (11 months)
Number of sites	Up to eight sites. Participating countries include Australia and New Zealand
Follow-up Schedule and Study Procedures	
Participants require follow-up through 90 (± 21) days after their last ELS procedure with interim visits at Day 1, 2, 3, 7 (± 1), 14 (± 4) and 30 (± 4) days
 
Pre-procedure testing (minimum):
 
 a. Urinalysis b. Urine culture c. Serum creatinine d. Computed Tomography (CT) scan (non-contrast) within the last 14 days showing location, radiodensity and size of stone e. Assessment of pain medication intake f. Pain assessment g. An x-ray KUB is recommended if participant is suspected to have radiolucent stones and CT scout film is not available or suitable for use

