	
During Procedure (up to 2 ELS treatments):
 
Cystoscopy with local anaesthesia and light or moderate sedation or light general anaesthesia (investigator's discretion), placement of ureteral catheter, periodic fluoroscopic and/or diagnostic ultrasound imaging (at investigator's discretion), intraluminal ureteral placement of ELS Acoustic Enhancer material and administration of acoustic energy. Multiple repetitions of ELS Acoustic Enhancer placement-insonation cycle will be performed
 
Follow-up:
 
1, 2, 3, 7 days (telephone follow-up): Assess pain and pain medications, evaluate for AEs
 
14 (\pm 4) days (on site exam): KUB X-ray and ultrasound; physical exam; assess pain and pain medications; urine culture; evaluate for AEs; Assess for eligibility for 2nd ELS Treatment (i.e. treated stone/fragment is \geq 3 mm and subject remains eligible per I/E criteria)
 
30 (\pm 4) days after last ELS procedure: CT scan (non-contrast) to evaluate stone status; physical exam; assess pain and pain medications; evaluate for AEs; serum creatinine; Assess for eligibility for 2nd ELS Treatment
 
Treatment 2 (if necessary): Repeat ELS treatment if subject meets eligibility criteria (i.e. treated stone/fragment is \geq 3 mm and subject remains eligible per I/E criteria). If performed, repeat Day 1, 2, 3, 7, 14 & 30 Follow-Up visits
 
90 (\pm 21) days: physical exam; serum creatinine; evaluate for AEs and record medications; renal-bladder ultrasound for safety assessment

Primary Endpoint	Treatment success: Proportion of study participants who, after up to 2 ELS treatments, have a complete absence of stones or with any residual fragments measuring less than 3 mm in the largest dimension as assessed by follow-up imaging through 30 day follow-up after last ELS procedure
Secondary Endpoints	
 • Proportion of participants with Serious Device and/or Serious Procedure-Related AEs from initial ELS Treatment through 30 days following last ELS treatment • Proportion of participants with Serious Device and/or Serious Procedure-Related AEs from initial ELS Treatment through 90 days following last ELS treatment • All AEs & SAEs from initial ELS Treatment through 30 days following last ELS treatment • All AEs & SAEs from initial ELS Treatment through 90 days following last ELS treatment • Participant satisfaction at 30 day follow-up following last ELS treatment

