4.4 Screening and Enrollment Procedures

4.4.1 Eligibility review

Patients presenting with urinary stone disease will be screened for this study. Initial eligibility criteria for the study will be determined by the investigator based upon review of their medical history, presentation and diagnostic imaging. If the participant appears to meet the study criteria, then the investigator will explain the investigational treatment, provide information regarding the potential risks and benefits, explain the follow-up requirements and obtain written informed consent per the informed consent process.

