4.4.2 Informed consent process

The investigator, or authorised designee, is responsible for obtaining written informed consent from each participant using the IRB/EC approved consent form prior to initiation of any study specific assessments or procedures.

Potential study participants will be given adequate time to review the consent form, ask questions, and consider their options before being asked to sign the form. Informed consent shall be obtained under circumstances that minimise the possibility of coercion or undue influence. The information that is given to the participant shall be in language understandable to the participant. The participant will not be led to believe that they are waiving their rights as a study participant or the liability of the sponsor or investigator.

Study participants will be informed that the sponsor and regulatory authorities will have access to personally identifying information for the purposes of monitoring data against source documentation. However, all data stored and presented by the sponsor will be de-identified. The participant will be asked to sign one copy of the informed consent form. The original, signed document remains at the investigational site and a copy (or second signed original) is given to the participant.

If new information regarding the investigational device becomes available and/or the clinical investigational plan (CIP) changes and the information can significantly affect a participant's future health and medical care, participants will be informed of the information and may be asked to sign a revised informed consent form.

Any modification to the study sample informed consent form made by the Investigational Site must be approved by the sponsor and the IRB/EC before use. Each Investigational Site will provide the sponsor with a copy of the EC approved consent forms.

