11. STATISTICAL METHODS

11.1 Population to be analysed

Primary analyses of study data will include available data on all enrolled participants, referred to in International Conference on Harmonization document E9 (“Statistical Principles for Clinical Trials”) as the full analysis set. Study enrollment is defined as that time when the participant signs the informed consent form and is then eligible to begin screening assessments. Other study participants will be classified as screen failures.

Study analyses will then be conducted on two distinct cohorts of study participants: an intent-to-treat (ITT) analysis including all enrolled participants and all available data, and a per-protocol (PP) analysis including the subgroup meeting all inclusion and exclusion criteria and for whom treatment was performed according to the study protocol with follow-up through 30 days (or 14 days if no follow-up imaging was required beyond 14 days). Both ITT and PP analyses will be summarized and reported.

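### Exclusion criterion 11 counts the aspirin stop back from enrolment, which is the signing of consent, so a stop made for the study has to come before consent, and a second ELS has no reference point

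*Combined protocol and SAP*

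**What the plan says.** Criterion 11 in Section 4.3.2 has two sentences. The first excludes on coagulation grounds: "Participant has coagulation abnormality or taking prescription anticoagulants that cannot be stopped during treatment". The second deals with aspirin: "Aspirin (ASA) usage will be discontinued at least 7 days prior to enrollment at the discretion of the attending physician". The synopsis repeats the aspirin rule with the same reference point: "Aspirin usage will be discontinued at least 7 days prior to enrollment at the discretion of the attending physician".

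Enrolment has a fixed meaning in this protocol. Section 4.4.4 says "Enrollment is defined as that time when the participant signs the informed consent form", and Section 11.1 repeats it: "Study enrollment is defined as that time when the participant signs the informed consent form".

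Section 4.4.2 requires consent "prior to initiation of any study specific assessments or procedures". Before consent, Section 4.4.1 provides only for a review of existing information: "Initial eligibility criteria for the study will be determined by the investigator based upon review of their medical history", together with presentation and imaging.

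For a second ELS, Section 6.3.1 applies the Section 4.3 criteria again. The synopsis makes it a condition that the "subject remains eligible per I/E criteria". Section 6.3.2 recommends the second procedure 30 days (plus or minus 14) after the first. No section gives an aspirin interval measured from an ELS procedure. Section 6.2.1 refers to the IFU for the full procedure, and the IFU is not part of the documents.

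**The concern.** The aspirin rule is tied to the wrong event. A patient who is found to be taking aspirin at the history review, and whose physician wants it stopped for the study, can meet the clause only by stopping at least a week before signing the form. The medication change would then come before the agreement to take part. The first sentence of the same criterion refers to treatment, which suggests that the enrolment reference in the second was not deliberate.

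Two further consequences follow. Time between consent and the procedure is added to the 7 days, so aspirin may be off for longer than the rule needs. And because enrolment happens once, the clause says nothing usable about a second ELS. A participant who restarted aspirin after the first procedure still satisfies it as written.

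What is at stake is the order of consent and medication change, the length of an interruption, and a clear instruction at retreatment. The statistical conclusions are not at stake.

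**Working it through.** The plan states no figure on this point, so there is none to reproduce. The check is a reading of the text and day arithmetic.

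**Inputs**
- Stop at least 7 days before enrolment (4.3.2 and synopsis, criterion 11).
- Enrolment = signing of consent = day 0 (4.4.4, 11.1).
- Qualifying CT within 14 days before enrolment (4.3.1, criterion 4a) and within 14 days of ELS (6.1).
- Second ELS recommended at Day 30 plus or minus 14 after the index procedure (6.3.2).
- Visits at Day 14 plus or minus 4 and Day 30 plus or minus 4 (6.2.5, 6.2.6).

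**Order of stop and consent.** Stop day ≤ 0 - 7 = -7. Every stop that meets the clause lies at least 7 days before consent.

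**Index ELS.** Let the index ELS be e days after consent, with e ≥ 0. The latest permitted stop is 7 + e days before ELS, which is never less than 7. With a single CT, e runs from 0 to 14, so the distance runs from 7 + 0 = 7 to 7 + 14 = 21 days. Compared with a 7-day stop counted from the procedure, the excess is e, that is 0 to 14 days. This assumes that aspirin stays off until ELS. The verb in the clause can be read that way, but the text gives no end date.

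**Second ELS.** The recommended window is 30 - 14 = Day 16 to 30 + 14 = Day 44. The clause's latest stop date lies 7 + 0 + 16 = 23 to 7 + 14 + 44 = 65 days earlier. These are distances from the reference date. They do not measure aspirin exposure or bleeding risk, and the upper limits fail if the CT is repeated or the window is not kept.

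**Does the change fit the schedule?** Let the CT be a days old when aspirin is stopped, with a 7-day stop.
- Counting from the procedure, with consent and stop on the same day: ELS is at the earliest 7 days later, with the CT a + 7 days old. The condition a + 7 ≤ 14 gives a ≤ 7. At a = 8 the CT is 15 days old and must be repeated.
- Current wording: consent, and so ELS, can come at the earliest 7 days after the stop. The CT is then again a + 7 days old, and the limit is again a ≤ 7.
- Retreatment, stop started at the Day 14 visit (Day 10 to 18): ELS from 10 + 7 = Day 17 to 18 + 7 = Day 25.
- Retreatment, stop started at the Day 30 visit (Day 26 to 34): ELS from 26 + 7 = Day 33 to 34 + 7 = Day 41.
- Both retreatment ranges lie within Day 16 to 44.

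**The case against.** The clause orders no stop. It leaves the decision to an attending physician, who need not be the investigator. Section 4.4.2 speaks of assessments and procedures and does not name medication changes. Many aspirin users may already have stopped in ordinary care, and nothing in the protocol tells a site to stop aspirin for the study before consent. This stands as a limit on the point: it concerns only stops made for the study, the conflict is with the intent of Section 4.4.2 rather than its letter, and the number affected is unknown. It does not remove the point, because discretion over whether to stop leaves the written reference date where it is.

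A reader might infer a safety gap at the first procedure, since Section 7.1 lists bleeding, with transfusion in rare cases. The documents do not support that. A stop at least 7 days before consent is also at least 7 days before the index ELS if aspirin stays off, so on interval the current rule is at least as cautious as one counted from the procedure. Section 7.1 does not mention aspirin. Nor can it be said that sites have no aspirin guidance for the procedure day, because the IFU may give it.

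On retreatment, it can be argued that any criterion tied to enrolment needs sensible adaptation at a second procedure, and that consent has been given by then. Both are true. The consent issue therefore does not arise at the second ELS. The missing reference point does, because the criteria are expressly applied again and the aspirin clause can be met by a stop that has since been reversed.

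Medication recording is already covered by Section 6.1 and Table 2, so no fault is found there.

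**Conclusion.** The point holds as a minor drafting fault in a stated rule. Under the protocol's own definition of enrolment, an aspirin stop made for the study has to precede consent by at least 7 days. It may also last longer than needed (0 to 14 days of excess, with a single CT and aspirin kept off). At a second ELS the clause gives no usable reference point.

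This rests on the literal definition in Sections 4.4.4 and 11.1, and on the stop being made for the study. The size in participants cannot be given, because the documents do not state how many take aspirin. A reader might also look for an effect on the results. There is none on the primary test or the sample size, and the adverse event endpoints are descriptive.

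**What to change.** In Section 4.3.2 and in the synopsis, replace the reference to enrolment in the aspirin sentence with *prior to each ELS procedure*. Keep the 7-day minimum and the attending physician's discretion. Add one sentence: *Any aspirin stop made for the study, as distinct from one already made in ordinary care, follows signed consent.* Check that the IFU says the same. A field for the date of the last aspirin dose would be convenient but is optional.

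The cost is wording in two places. A participant found on aspirin at presentation may need a repeat CT, with extra radiation and some delay, if the CT is more than 7 days old when aspirin is stopped; otherwise the physician may choose not to stop it. As shown above, the same 7-day limit applies under the current wording, so little of this cost is new. Retreatment fits the recommended window whether the stop starts at the Day 14 or the Day 30 visit.
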